4.2. Stratification, Randomization, and Blinding

The study will be conducted in 2 stages for each disease cohort (Section 9.3 of the protocol). Subjects will be randomized with 1:1 ratio to receive subcutaneous azacitidine alone or subcutaneous azacitidine in combination with durvalumab.

The randomization procedure will be accomplished by a validated Interactive Response Technology (IRT). At randomization, subjects will be stratified by cytogenetic risk: very good, good, intermediate versus poor or very poor for the MDS cohort ([Appendix 17.4](#), IPSS-R Cytogenetic Risk Groups), and intermediate versus poor for the AML cohort ([Appendix 17.5](#)).

This study will employ dynamic randomization based on two stratification factors (defined above) to achieve an even treatment balance between (A) Combination and (B) Monotherapy.

Step 1: Determine Primary (Disease Type) and Secondary (Cytogenetic Risk Factor) Stratification Factors

Subjects will first be stratified based on the disease type of either MDS or AML, as the secondary stratification factor variable depends on this information. Once disease type has been identified, the secondary stratification factor of cytogenetic risk factor can be identified. Cytogenetic risk factor options for each disease type are as follows:

- MDS: Very good, good and intermediate vs. Poor and Very Poor
- AML: Intermediate vs. Poor

Step 2: Determine Evaluable Subjects

Only evaluable subjects will be considered when dynamic randomization is performed. Evaluable subjects are those who have been randomized and NOT been marked as replacement eligible via the Replacement Eligibility Review admin module.

Step 3: Determine Set of Ranges

To achieve treatment balance the measure of variability needs to be defined and is a quantitative way to describe the imbalance of patients amongst the treatment arms. Specifically, the measure of variability for this procedure is the Range which is the difference between the number of patients in the treatment arm with the most patients and the number of patients in the treatment arm with the least patients. For example, if treatment A has 4 patients and treatment B has 3 patients, the Range is 1, ie, 4 (maximum) – 3 (minimum). When a new subject is to be randomized, the potential Ranges will be calculated for each possible treatment assignment. This will provide a Set of Ranges that measures the potential imbalance resulting from assigning a patient to the different treatments.

For example, the current enrollment (of evaluable subjects) for the MDS disease type is:

	Treatment A	Treatment B
Total Randomized	6	5
Level/Stratum Balance		
Intermediate	4	3
Poor and Very Poor	2	2

The next subject to be randomized has disease type MDS and is Intermediate cytogenetic risk. First step is to calculate the Set of Ranges for the Intermediate level.

If the subject were to be assigned to treatment A the totals would become 5 and 3 and the intermediate level range would be 2, as calculated by Treatment A – Treatment B = 2.

	Treatment A	Treatment B
Intermediate	5	3

If the subject were to be assigned Treatment B the Range would be $4 - 4 = 0$ for the strata.

	Treatment A	Treatment B
Intermediate	4	4

Step 4: Determine the Rank

Continuing with the above example, since Treatment B has the lowest Range, it receives Rank 1 and Rank 2 would be assigned to Treatment A.

Step 5: Determine the Appropriate Cumulative Representation

Using the tables below and considering that in the scenario above, Rank 1 \diamond Rank 2 we would reference Rank Scenario 4 to determine the appropriate Cumulative probabilities. Ultimately based on this Rank Scenario the probability to randomize the patient to treatment A or B will be 1/1 if there is no difference in Rank (Rank Scenario 1 below). Otherwise, the probability will be 9/1 – with the treatment defined as Rank 1 above receiving the higher probability (Rand Scenario 2 below).

Rank Scenario 1: Rank 1 = Rank 2

Rank	Probability	Decimal Probability	Cumulative Probability
Rank 1	1/2	0.5	0.5
Rank 2	1/2	0.5	1.0

Rank Scenario 2: Rank 1 \diamond Rank 2

Rank	Probability	Decimal Probability	Cumulative Probability
Rank 1	9/10	0.9	0.9
Rank 2	1/10	0.1	1.0

Step 6: Query the Random Number table

A table is required that contains a sequence of random numbers between 0.0000 and 1.0000. This list should be uniformly distributed. Based on the next unassigned random number on the list. If the number is \leq Rank 1 cumulative probability, then the treatment in Rank 1 gets the assignment. If the number is $>$ Rank 1 cumulative probability then the treatment in Rank 2 gets the assignment.

Blinding : not applicable for this study.

4.3. Sample Size

A total of approximately 182 eligible subjects will be enrolled in the study, with a total of 72 subjects in the MDS cohort and 110 subjects in the AML cohort.

A subject who discontinues from the treatment phase before the first postbaseline efficacy assessment (following treatment Cycle 3) will be replaced unless the subject had a documented progression of their disease or died from their disease or died from an IP-related event. An additional subject will be included in that cohort (MDS or AML cohort).

4.3.1. MDS Cohort

Sekeres et al ([Sekeres, 2014](#)) demonstrated that treating subjects with higher-risk MDS resulted in an overall response rate (ORR) (complete remission [CR], marrow complete remission [mCR], partial remission [PR], hematological improvement [HI]) of 36% after four cycles of azacitidine alone. This number is consistent with the “HI and better” rate from the AZA-MDS-001 trial of 36.4%.

Assuming a treatment effect of 100% relative improvement of ORR (from 36% to 72% ORR), a sample size of 72 subjects will provide a power of 90% to detect such an effect at the 5% level of statistical significance.

An interim analysis for futility purpose will be conducted on the first 30 subjects who have completed 6 cycles of treatment unless they have established an earlier response (CR, mCR, PR or HI) or discontinued due to death or disease progression. Subjects assigned to Arm A, who received less than 3 cycles of durvalumab and continued under azacitidine monotherapy are to be excluded from the interim analysis.

The MDS cohort will continue to enroll a total of 72 MDS subjects if one of the below conditions is met at the interim analysis:

- If the ORR (considering the composite score of CR + PR + mCR + HI) in the combination arm is numerically higher than or equal to the control group (azacitidine alone) or,
- If the response rate of one of the components of this composite score (in particular CR rate) in the combination arm is numerically higher than or equal to the control group (azacitidine alone) or,
- If evidence of a clinically meaningful difference in favor of the combination arm in a secondary endpoint (eg, duration of response) is provided.

If none of these conditions is met, then the cohort might be terminated. The data monitoring committee (DMC) will review the data at the time of interim analysis and will provide recommendation/advice to Celgene.

4.3.2. AML Cohort

Studies conducted by Dombret et al and Fenaux et al ([Dombret, 2015](#); [Fenaux, 2010](#)) showed a response (CR + complete remission with incomplete blood recovery [CRi]) rate of 25% in AML subjects treated with azacitidine. Assuming a treatment effect of 100% relative improvement of CR and CRi (from 25% to 50% absolute CR and CRi rates), a sample size of 110 subjects will provide a power of 80% to detect such an effect at the 5% level of statistical significance.

An interim analysis for futility purpose will be conducted on the first 50 subjects who have completed 6 cycles of treatment unless they have established an earlier response (CR or CRi) or discontinued due to death or disease progression. Subjects assigned to Arm A, who received less than 3 cycles of durvalumab and continued under azacitidine monotherapy are to be excluded from the interim analysis.

The AML cohort will continue to enroll a total of 110 AML subjects if one of the below conditions is met at the interim analysis:

- If the ORR (considering the composite score of CR + CRi) in the combination arm is numerically higher than or equal to the control group (azacitidine alone) or,
- If the response rate of one of the components of this composite score (in particular CR rate) in the combination arm is numerically higher than or equal to the control group (azacitidine alone) or,
- If evidence of a clinical meaningful difference in favor of the combination arm in a secondary endpoint (eg, duration of response) is provided.

Durvalumab (MEDI4736)

Statistical Analysis Plan: Protocol MEDI4736-MDS-001 _____ Celgene Corporation

If none of these conditions are met, then the cohort might be terminated. The DMC will review the data at the time of interim analysis and will provide recommendation/advice to Celgene.

CELGENE PROPRIETARY INFORMATION

5. GENERAL STATISTICAL CONSIDERATIONS

5.1. Reporting Conventions

Summary tables, listings, and any supportive SAS output will include a “footer” of explanatory notes that will indicate, at a minimum, the following:

- Program source (eg, SAS program name, including the path, that generates the output) and
- Data extraction date (eg, the database lock date, run date)

The purpose of the data extraction date is to link the output to a final database, either active or archived, that is write-protected for replication and future reference. An output date will also appear on each output page and will indicate the date the output was generated by the analysis program. Individual source listings will display all the relative values supporting corresponding table and figure.

5.1.1. Dates Handling

Dates will be stored as numeric variables in the SAS analysis files and reported in DDMMYYYY format (ie, the Date9 datetime format in SAS). Dates in the clinical database are classified into the categories of procedure dates, log dates, milestone dates, outcome dates, and special dates.

- **Procedure Dates** are the dates on which given protocol-specified procedure are performed. They include the dates of laboratory testing, physical examinations, bone marrow aspirates or biopsies, etc. They should be present whenever data for a protocol-specified procedure is present and should only be missing when a procedure is marked as NOT DONE in the database. Procedure dates will not be imputed.
- **Log Dates** are dates recorded in the case report form (CRF) data logs. Specifically, they are the start and end dates for adverse events and concomitant medications/procedures. They should not be missing unless an event or medication is marked as *ongoing* in the database. Otherwise, incomplete log dates will be imputed according to the rules in [Appendix 17.1](#) (eg, for duration or cycle assignment etc). However, in listings, log dates will be shown as recorded without imputation.
- **Milestone Dates** are dates of protocol milestones such as randomization, study drug start date, study termination, etc. They should not be missing if the milestone occurs for a subject. They will not be imputed.
- **Outcome Dates** are dates corresponding to study endpoints such as survival, progression, etc. In most cases they are derived either from a milestone (eg, the survival date is derived from the death date), or a procedure date (eg, the progression date is derived from the date of the tumor scan that was used to determine progression). They may be subject to endpoint-specific censoring rules if the outcome did not occur, but are not otherwise subject to imputation.

- **Special Dates** cannot be classified in any of the above categories and they include the date of birth. They may be subject to variable-specific censoring and imputation rules (see [Section 5.1.2](#) below).

Dates recorded in comment fields will not be imputed or reported in any specific format.

5.1.2. Calculations Using Dates

Calculations using dates (eg, subject's age or relative day after the first dose of study medication) will adhere to the following conventions:

- Study days after the start day of study drug will be calculated as the difference between the date of interest and the first date of dosing of study medication plus 1 day. The generalized calculation algorithm for relative day calculations will be [date of interest – treatment start date + (date of interest >= treatment start date)]. This calculation will result in dates prior to the treatment start date being presented as negative days, and those occurring on or after the treatment start date as Day 1 or later, ie, there will be no Day 0. Note: Partial date for the first study drug is not imputed in general. All effort should be made to avoid incomplete study drug start date.
- Age (expressed in days) is calculated:
 $AGE = DATE \text{ of informed consent} - DATE \text{ of BIRTH} + 1$. In practice, age will be transformed into years by dividing the difference by 365.25 days, then truncating.
 - Using calculated age from the clinical database is preferred. When not available, the calculated/reported age from the CRFs or interactive voice response system (IVRS) may be used
 - Partial birth date: impute missing day as 15th of the month; impute missing month as July; set age as missing if missing year
- Intervals that are presented in weeks will be transformed from days to weeks by using (without truncation) the following conversion formula:
 $WEEKS = DAYS / 7$.
- Intervals that are presented in months will be transformed from days to months by using (without truncation) the following conversion formula:
 $MONTHS = DAYS / 30.4375$.

5.1.3. Calculation of Cycles

The start date of each treatment cycle will be calculated based on study drug exposure records for each subject. The start date of the first cycle will be the date when the subject receives any dose of study drug. First dose date of Durvalumab infusion or azacitidine injection in each cycle will be considered as the start of the cycle.

Once the start dates, eg, $S_1, S_2, S_3 \dots$ are calculated, the end date of each cycle is calculated as the day before the start date of the following cycle, ie, $E_i = S_{i+1} - 1$. The last cycle in the treatment

phase is defined as the cycle with the last dose of any study drug. For the last cycle, the end date will be the last dose date plus 28 days or the death date, whichever is earlier.

The cycle number for each date of interest, eg, AE or lab, will be calculated based on the cycle window set by their start and end dates. If a date is on or after S_i and before S_{i+1} , the corresponding cycle number will be i .

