### 7.2.1.1. Azacitidine Dispensation and Administration

Azacitidine will be administered on Days 1 to 7 of each treatment cycle. The subject may not receive IP for each treatment cycle until all Day 1 procedures have been completed.

Vials/syringes should be used for the specific subjects to whom they are assigned, and must not be shared between subjects.

For FCBP subjects, a pregnancy test must be performed, and a negative result verified by the Investigator, within 72 hours prior to IP administration on Day 1 of each treatment cycle.

Subjects will receive azacitidine 75 mg/m^2/day subcutaneous for 7 days (Days 1 to 7) every 28 days. In the event 2 or fewer doses are missed during the 7-day dosing period, dosing should continue so the subject receives the full 7 days of therapy. If 3 or more days are missed during the 7-day dosing period, the Investigator should contact the sponsor and a decision on dosing will be made on a case-by-case basis.

Subjects assigned to the combination treatment arm will have azacitidine administered on Day 1 of each treatment cycle approximately one hour after completion of the durvalumab infusion, after resolution of any related AE immediately after durvalumab infusion, if any.

If the dose of azacitidine is modified during the course of the study (Section 7.2.2.1) and benefit is demonstrated at a dose lower than 75 mg/m^2, that dose should be maintained during subsequent cycles that are given (unless toxicity develops).

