8.1. Treatment Exposure and Duration

Treatment exposure and number of days dosed will be summarized. Total treatment exposure (days) for each study drug is defined as follows:

- Azacitidine: date of first dose through date of last dose + 28 days;
- Durvalumab: date of first dose through date of last dose + 90 days.

Treatment exposure for subjects in the azacitidine alone arm is same as the treatment exposure of azacitidine. Treatment exposure for subjects in the combination arm is defined as date of first dose of any study drug through later one of date of last dose azacitidine + 28 days and date of last dose durvalumab + 90 days. Duration of exposure will be summarized for each arm.

Total number of days dosed is defined as the total number of days with a nonmissing dosing date.

See [Section 5.1.3](#) for cycle definition. Average cycle length (days) and number of treatment cycles will be summarized for each study drug. For azacitidine, average number of days dosed per cycle will be summarized. The number of days dosed per cycle is defined as the number of days with a nonmissing dosing date within that cycle. For average cycle length and average number of days dosed per cycle, a single average value will be computed for each subject and then the descriptive statistics will be provided. Additionally, the count and percent of subjects by number of cycles of treatment will be provided for each treatment.

For each study drug, duration of treatment (days) is defined as:

- (study drug end date) – (date of Cycle 1 Day 1) + 1.

Study drug end date is defined as Min [last non-zero/non-missing dose date + number of days to be covered by the last dose, death date].

The number of days to be covered by the last dose is defined in the [table 3](#).

Table 3: Number of days to be covered by the last dose

IP	Schedule	n = days to be covered by the actual last dose (if schedule respected) *
Durvalumab	CxD1	n=27
Azacitidine	CxD1 to CxD7	n=21

* if schedule is not respected the number of days to be covered by the actual last dose will be adapted accordingly so that the last dose date + n corresponds to the study day 28 of the cycle.

8.2. Cumulative Dose:

The cumulative dose during the treatment is defined as the sum of all doses taken across the treatment period (in mg). Cumulative dose will be calculated separately for azacitidine and durvalumab.

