8.5. Dose Intensity

For each cycle, dose intensity for a study drug is defined as the cumulative dose of the study drug in the cycle divided by the cycle length. The overall dose intensity for each study drug is defined as the cumulative dose divided by the total length of cycles in treatment duration. A single average value will be computed for each subject, overall and within each cycle, and then the descriptive statistics will be computed for each treatment group.

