8.6. Relative Dose Intensity

Relative dose intensity is defined as the actual dose intensity divided by the planned dose intensity;

- For durvalumab, the planned dose intensity (mg/day) is 1500 mg / 28 days.

- For azacitidine, the planned dose intensity (mg/day) is $75 \text{ mg/m}^2 * 7$ multiplied by the subject's BSA (m^2) / 28 days.

Descriptive statistics of overall and by cycle relative dose intensity will be summarized. Additionally, the number and percentage of subjects will be summarized by category such as $\leq 85\%$ and $> 85\%$ for relative total dose intensity of azacitidine, durvalumab, the actual category can be data driven.

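### SAP 5.1.3 ends the last cycle 28 days after the last dose or at death, so relative dose intensity of a fully dosed final azacitidine cycle reads 80% in a survivor and over 100% after an early death

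*SAP*

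**What the plan says.** - **Cycle length (SAP 5.1.3).** For cycles before the last, "the end date of each cycle is calculated as the day before the start date of the following cycle". The last cycle in the treatment "phase is defined as the cycle with the last dose of any study drug", so in the combination arm one cycle length serves both drugs. Its end is set separately: "For the last cycle, the end date will be the last dose date plus 28 days or the death date, whichever is earlier".
- **Dose intensity (SAP 8.5).** By cycle, "dose intensity for a study drug is defined as the cumulative dose of the study drug in the cycle divided by the cycle length". Overall, it is the cumulative dose over the total length of cycles in treatment duration.
- **Relative dose intensity (SAP 8.6).** Actual over planned intensity, reported by cycle and overall. "For durvalumab, the planned dose intensity (mg/day) is 1500 mg / 28 days". The azacitidine plan is 75 mg/m² × 7 × BSA, also over 28 days.
- **Treatment duration (SAP 8.1, Table 3).** The last azacitidine dose covers 21 days and the last durvalumab dose 27, adapted if the schedule slips "so that the last dose date + n corresponds to the study day 28 of the cycle". The study drug end date is that day or death, whichever comes first.
- **Dosing (Protocol 7.2.1.1).** "Azacitidine will be administered on Days 1 to 7 of each treatment cycle". If one or two doses are missed, "dosing should continue so the subject receives the full 7 days of therapy".

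**The concern.** The numerator and denominator of RDI use different clocks. The plan assumes a 28-day cycle, but the observed last cycle is stretched by 7 days in a survivor who took azacitidine on schedule and is cut short in a subject who dies. A subject who received everything planned can therefore read well below or well above 100%, for reasons unrelated to the dose given. Early stopping and early death are both plausible in this population, so the affected cycles are not a curiosity.

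Table 3 also ends the same period on a different day. Two programmers following the SAP could produce different exposure tables.

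**Working it through.** **1. The SAP's own figure.** In Table 3 a fully dosed azacitidine cycle ends on Day 7 + 21 = Day 28, and durvalumab on Day 1 + 27 = Day 28. The two agree with each other and with the 28-day plan.

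**2. The 5.1.3 rule.** With the last azacitidine dose on Day 7, the cycle ends on Day 7 + 28 = Day 35. Length is counted inclusively, which matches the rule for earlier cycles (28 days when on schedule).

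**3. By-cycle RDI of the last cycle.** When the full dose D is given, RDI = (D / L) / (D / 28) = 28 / L, where L is the cycle length.

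| Final cycle, all planned doses given | L | RDI |
|---|---|---|
| Survivor, 7th azacitidine dose on Day 7 | 35 | 80.0% |
| Durvalumab given in that same cycle | 35 | 80.0% |
| Survivor, 7th dose on Day 8 (one dose made up) | 36 | 77.8% |
| Survivor, 7th dose on Day 9 (two doses made up) | 37 | 75.7% |
| Durvalumab-only cycle, survivor (Day 1 + 28) | 29 | 96.6% |
| Death on Day 10 | 10 | 280% |
| Death on Day 14 | 14 | 200% |
| Death on Day 28 | 28 | 100% |

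The Day 8 and Day 9 rows assume that missed doses are added directly after Day 7. If length were taken as end minus start, the first row would be 28/34 = 82.4%.

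**4. Overall RDI on 5.1.3 lengths.** For k fully dosed, on-schedule cycles, a survivor reads 28k / (28(k − 1) + 35). A subject who dies on Day 10 of cycle k reads 28k / (28(k − 1) + 10).

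| k | Survivor | Death on Day 10 of last cycle |
|---|---|---|
| 1 | 80.0% | 280% |
| 2 | 88.9% | 147.4% |
| 3 | 92.3% | 127.3% |
| 6 | 96.0% | 112.0% |
| 12 | 98.0% | 105.7% |

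**5. Overall RDI on Table 3.** If treatment duration in 8.5 means the duration defined in 8.1, the survivor's last cycle is 28 days and overall RDI is 100% for every k. The death column does not change, because 8.1 also stops at death.

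**6. The 85% category.** On 5.1.3 lengths, the rule alone moves a fully dosed survivor to 85% or less only at k = 1. For dose-reduced, on-schedule survivors, true RDI up to 0.85/0.889 = 95.6% (k = 2), 0.85/0.923 = 92.1% (k = 3) or 0.85/0.960 = 88.5% (k = 6) would be placed there.

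**7. Effect on arm means, as an illustration.** Assume everyone is fully dosed, the stopping probability per cycle is constant, the maximum is 12 cycles and 5.1.3 lengths apply. True RDI is then 100% throughout.

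| Stopping per cycle | No deaths | 5% to 20% of last cycles ending in a Day-10 death |
|---|---|---|
| 8% | 94.8% | 96.4% to 101.1% |
| 20% | 91.3% | 94.4% to 103.6% |

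Without deaths, the spurious gap between these two stopping rates is 94.8 − 91.3 = 3.5 points. Deaths push the other way and can offset or reverse it.

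**The case against.** The strongest reply is that little rests on RDI. The safety endpoint in SAP Table 2 names adverse events and laboratory evaluations, not RDI, and no test on RDI is planned. Cumulative dose (8.2), average daily dose (8.3), compliance (8.4), dose modifications (8.7) and adverse events leading to discontinuation (12.1) do not divide by cycle length. The rule is the same in both arms. The 5.1.3 window also has a sensible use: it assigns adverse events and laboratory dates to cycles, and 28 days matches the azacitidine adverse-event window in 12.1. The 85% cut is only an example, and 8.6 allows the categories to be data driven. All of this stands, and it limits the consequence. It does not make the by-cycle figure right.

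Four stronger readings are tempting, but the documents do not support them:

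- **That the tolerability comparison between arms is wrong.** A common rule distorts the difference only if the arms differ in cycles received or in timing of early deaths, and nothing in the documents shows that they do.
- **That a final cycle always reads 80%.** Durvalumab-only final cycles, which Protocol 3.2.2 permits, and final cycles with made-up doses give other values.
- **That adopting Table 3 would cure the problem.** Its end date also stops at death, so a Day-10 death would still read 280%.
- **That a large share of AML subjects would show values such as 200% or 280%.** Protocol 1.3.3 gives a 10.4-month median survival on azacitidine from another trial, in AML with more than 30% blasts. Under an assumed constant hazard, deaths within 28 days (0.92 months) are 1 − 0.5^(0.92/10.4) ≈ 6%, or 6 to 7 of 110. Later deaths are diluted by earlier cycles in overall RDI.

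**Conclusion.** The rule is wrong as written for one planned output and ambiguous for another. By-cycle RDI of a fully dosed, on-schedule final azacitidine cycle reads 80% in a survivor, and durvalumab given in that cycle also reads 80%. After a death before Day 28 it exceeds 100%. These figures follow directly from 5.1.3, 8.5 and 8.6 and need no assumption beyond inclusive day counting. Overall RDI is either biased downward in survivors, by 20 points at one cycle and 4 points at six, or unbiased in them, depending on whether 5.1.3 or Table 3 governs treatment duration. The SAP does not say which. The upward error after early death occurs on both readings.

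The consequence is limited to a descriptive exposure summary. The 3.5-point gap between arms is an illustration under stated assumptions, not an estimate for this trial. The point concerns an exposure calculation only, not how either drug is given.

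**What to change.** In SAP 8.5 and 8.6, state that the last-cycle length used for dose intensity and RDI, both by cycle and overall, is a nominal 28 days for all subjects, including those who die in that cycle. A fully dosed final cycle then reads 28/28 = 100% whether or not the subject dies. Keep actual lengths for earlier cycles, so that delays still lower the intensity. Keep the 5.1.3 end date of last dose plus 28 days for assigning adverse events and laboratory dates to cycles, and say that it serves that purpose only.

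The cost is one sentence in the SAP and a small programming change. No data collection, protocol text or dosing instruction is affected.
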